### Questionnaire Administration

Eligible dentists will be identified from their responses to the Enrollment Questionnaire. Although unlikely, responses from dentists who do not meet eligibility criteria but who still are asked to complete the questionnaire will be removed prior to statistical analyses.

A waiver of documentation of signed informed consent for participants who complete the electronic or paper questionnaire will be requested. Consistent with regulations outlined by the University of Alabama (UAB) IRB, information about the study will be provided to all eligible dentists in the postal invitation mailing as well as in the electronic or paper questionnaire prior to the start of the questionnaire questions. Completion of the questionnaire will indicate tacit consent.

The questionnaire will be administered by the CC. An initial study invitation email will be sent to approximately 2,300 eligible practitioners by the CC on behalf of the RCs over a period of three to four months. The invitation will include information regarding the study. A follow-up postal letter on National Dental PBRN stationery will be mailed to inform the dentists that they received an email with a link to the electronic version of the questionnaire to complete. Dentists will be informed that ideally the questionnaire must be completed in one-sitting (although they will be given an option to save and complete the questionnaire at a later time) and that it will take up to 30 minutes to complete. Practitioners will receive multiple reminders to complete the questionnaire. Those who do not respond to email invitations will be mailed paper versions of the questionnaire.

Both electronic and paper versions of the questionnaire will be used to increase participation rates. Practitioners will be encouraged to visit the secure web site to complete the questionnaire. Questionnaires completed on paper will be sent to the CC and entered into the secure web site by CC study personnel.

If no feedback is received or the practitioner does not complete the electronic or paper version of the questionnaire after multiple follow up attempts over a period of three to four months, it is assumed the practitioner is not interested in the study.

## **7.2 Stage 2 Study Procedures/Evaluations**

The practitioner and staff will undergo training for the clinical component of the study. The goals of the study, inclusion/exclusion criteria, CRF and other documentation will be explained. In

addition, the practitioner will approach and confirm the participation of his/her dental laboratory or laboratories.

The laboratory will undergo training for the clinical portion of the study. After participation is confirmed (i.e., email, verbally) by the RC, goals of the study will be explained and training on the study and completion of the Laboratory Evaluation of Case questionnaire will be conducted. Training will detail study goals, provision of tacit consent when completing the questionnaire, and procedures for maintaining confidentiality.

A potential patient may be recruited at any dental visit, not just examination or recall visits. When it is determined that a patient may be eligible for study participation, the designated office personnel trained in human subjects protection will introduce the study to the patient and will ascertain that inclusion criteria are met.

For patients who express interest in participating in the study, a designated office individual trained in human subjects protection will initiate the consent process with the patient and ensure that the consent document has been executed. It is anticipated that in most cases this will be the dentist. At this time patient demographic information will be recorded on the Patient Characteristics CRF and submitted to the RAS.

After entry into the study, a patient will undergo a baseline visit that will involve routine patient care for crown preparation. Data regarding the patient, tooth and clinical environment (after visual assessment of the tooth, supporting structures and occlusion), crown preparation procedure, and impression procedure and materials will be recorded on the “Crown Preparation” CRF for each patient and submitted to the RAS. Then, at the crown insertion appointment, data related to the crown fit and crown adjustments, if warranted, will be recorded. The practitioner completes the CRF “Crown Insertion” and submits it to the RAS.

Practitioners are required to send the crown impression and supporting materials to the lab(s) that have agreed to participate in the study. Upon receipt and assessment of the crown impression and supporting materials (e.g., bite registration, opposing impression or cast), dental laboratory technicians will record data related to technical aspects of the impression and supporting materials on the “Laboratory Evaluation of Case” questionnaire. For practitioners who use Optical Scanners (e.g. CEREC) along with a commercial lab and/or in-office milling, their digital files will be transmitted to an independent laboratory technician to review; this technician will complete the dental laboratory questionnaire. In order to maintain confidentiality of the technicians to allow truthful responses and not intentionally jeopardize the professional/business relationship with the practitioner, the technician (or designee) will mail the completed questionnaire to the RAS.

## 8 ASSESSMENT OF SAFETY

### 8.1 Specification of Safety Parameters

Safety monitoring for this study will focus on unanticipated problems (UP) involving risks to participants, including unanticipated problems that meet the definition of a serious adverse event.

#### 8.1.1 *Unanticipated Problems*

The Office for Human Research Protections (OHRP) considers UPs involving risks to patients or others to include, in general, any incident, experience, or outcome that meets **all** of the following criteria:

- Unexpected in terms of nature, severity, or frequency given (a) the research procedures that are described in the protocol-related documents, such as the IRB-approved research protocol and informed consent document; and (b) the characteristics of the patient population being studied;
- Related or possibly related to participation in the research (possibly related means there is a reasonable possibility that the incident, experience, or outcome may have been caused by the procedures involved in the research); and
- Suggests that the research places patients or others at a greater risk of harm (including physical, psychological, economic, or social harm) than was previously known or recognized.

#### 8.1.2 *Serious Adverse Events*

A serious adverse event (SAE) is one that meets one or more of the following criteria:

- Results in death
- Is life-threatening (places the patient at immediate risk of death from the event as it occurred)
- Results in inpatient hospitalization or prolongation of existing hospitalization
- Results in a persistent or significant disability or incapacity
- Results in a congenital anomaly or birth defect

An important medical event that may not result in death, be life threatening, or require hospitalization may be considered an SAE when, based upon appropriate medical judgment, the event may jeopardize the patient and may require medical or surgical intervention to prevent one of the outcomes listed in this definition.

### 8.2 Reporting Procedures

Incidents or events that meet the OHRP criteria for UPs require the creation and completion of an unanticipated problem report form. OHRP recommends that investigators include the following information when reporting an adverse event, or any other incident, experience, or outcome as an UP to the IRB:

- Appropriate identifying information for the research protocol, such as the title, investigator's name, and the IRB project number;
- A detailed description of the adverse event, incident, experience, or outcome;
- An explanation of the basis for determining that the adverse event, incident, experience, or outcome represents an UP;

- A description of any changes to the protocol or other corrective actions that have been taken or are proposed in response to the UP.

To satisfy the requirement for prompt reporting, UPs will be reported using the following timeline:

- UPs that are serious adverse events will be reported to the IRB and to NIDCR within 1 week of the practitioner becoming aware of the event.
- Any other UP will be reported to the IRB and to NIDCR within 2 weeks of the practitioner becoming aware of the problem.
- All UPs should be reported to appropriate institutional officials (as required by an institution's written reporting procedures), the supporting agency head (or designee), and OHRP within one month of the IRB's receipt of the report of the problem from the practitioner.

All UPs will be reported to NIDCR's centralized reporting system via Rho Product Safety:

- Product Safety Fax Line (US): [name]
- Product Safety Fax Line (International): [contact]
- Product Safety Email: [rho\\[contact]](mailto:[contact])

General questions about SAE reporting can be directed to the Rho Product Safety Help Line (available 8:00AM – 5:00PM Eastern Time):

- US: [name]
- International: [contact]

## **9 STUDY OVERSIGHT**

Stage 1: The GPI and SPI will be responsible for study oversight, including monitoring safety, ensuring that the study is conducted according to the protocol and ensuring data integrity. The SPI will review the data for safety concerns and data trends at regular intervals, and will promptly report to the IRB and NIDCR any UP, protocol deviation, or any other significant event that arises during the conduct of the study.

Stage 2: In addition to the PI's responsibility for oversight, study oversight will be under the direction of the NIDCR Medical Monitor. The PI will submit a report every 6 months to the NIDCR Medical Monitor for review. This report will include data regarding enrollment and retention, unanticipated problems and protocol deviations, outcome measures, quality management findings and other relevant parameters. If necessary, additional steps may be taken to ensure data integrity and protocol compliance.

## 10 CLINICAL SITE MONITORING

### Stage 1 – Practitioner Questionnaire

Clinical site monitoring will not occur for this survey component of the study. The CC is responsible for launching the survey and collecting data received as part of the survey. Quality assurance (QA)/Quality Control (QC) activities associated with data collection and processing will be outlined in the data management plan (DMP). The CC will ensure that the quality and integrity of study data and data collection are maintained, as detailed in the DMP. The RCs will be responsible for following up with eligible dentists who are considered non-respondents (see Section 6) to encourage study participation.

### Stage 2 – Clinical Component

Clinical site monitoring is conducted to ensure that the rights of human subjects are protected, that the study is implemented in accordance with the protocol and/or other operating procedures, and that the quality and integrity of study data and data collection methods are maintained. The network RAS will be responsible for clinical site monitoring for this study. RCs at each RAS will provide study training to practitioner sites and perform clinical site monitoring activities, to evaluate study processes and documentation based on NIDCR standards and principles of good clinical practice.

Quality management procedures are detailed in the protocol, Section 13 and the National Dental PBRN Manual of General Operations, Section 10. If concerning trends or other issues are identified through quality management activities, For-Cause, in-office clinical monitoring will be conducted. The general guidelines for conducting in-office monitoring for the network's observational clinical studies are documented in the network's Clinical Monitoring Plan in Section 11 of the National Dental PBRN Manual of General Operations. Documentation of monitoring activities and findings will be provided to the practitioner, GPI, and SPI, and aggregate reporting will be provided to NIDCR via [NIDCR\\[contact]](mailto:[contact]). NIDCR reserves the right to conduct independent audits as necessary.

---

## 11 STATISTICAL CONSIDERATIONS

### 11.1 Study Hypotheses

Primary objective: (1) Estimate the percentage of single-unit crowns deemed acceptable by the practitioner at clinical try-in, and (2) identify factors associated with crown success.

For this portion of the primary objective, the focus will be on estimation rather than hypothesis testing. We will obtain reliable and precise estimates (as determined by the width of the 95% confidence interval for the estimate) of the percentage of crowns that are deemed acceptable (upon receipt from laboratory and at time of clinical try-in). Second, we will test the hypothesis that there are factors (related to prosthodontic technique, patient/clinical, and practitioner) associated with crown acceptability. The null hypothesis for part (2) of this objective is that there is no association between prosthodontic techniques, patient/clinical characteristics or dentist characteristics and the rating of a crown as acceptable. This hypothesis will be explored using adjusted two-way tables and multivariable statistical models.

Secondary objective: (1) Quantify the prevalence of different methods and procedures utilized with crown preparations, and (2) explore whether these methods are significantly associated with dentist and practice characteristics.

The purpose of quantifying prevalence is for estimation rather than hypothesis testing. We will obtain reliable and precise estimates of the frequency of use of the various methods and procedures listed above. Furthermore, we will examine the relationship between the likelihood of using these methods and the characteristics of the dentist (e.g., age, gender, full-time vs. part-time) and practice (e.g., geographic location, urban vs. rural). The hypothesis is that there are variations in the use of methods and procedures for preparing crowns that are associated with dentist and practice characteristics. The null hypothesis for part (2) of this objective is that differences in dentist and practice characteristics do not explain variation in the use of particular methods and procedures. This hypothesis will be explored using unadjusted two-way tables and multivariable statistical models.

Secondary objective: (3) Estimate the percentage of single-unit crown preparations, impressions, and opposing casts deemed optimal by the dental laboratory, and (4) examine if this laboratory rating is associated with practitioner acceptability.

As the focus for (3) will be on estimate rather than hypothesis testing, estimates of the percentage (and 95% confidence interval) of patients with optimal materials received by the laboratory will be computed. For (4), we will test the hypothesis that the laboratory rating is associated with whether or not the crown is deemed acceptable by the practitioner at clinical try-in. The primary null hypothesis is that there is no association between laboratory rating and whether or not the crown is deemed acceptable by the practitioner at clinical try-in. Additional null hypotheses are that prosthodontic technique factors, patient/clinical factors, and dentist factors are not associated with laboratory ratings of crowns as optimal.

These data will be further analyzed by comparing the prosthodontic technique factors, patient/clinical factors, and dentist factors associated with primary objective (2). We will test the hypothesis that these factors are associated with an increased risk of optimal laboratory ratings.

This hypothesis will be tested using unadjusted two-way tables and multivariable statistical models.

[figure not shown]
Information collected in Phase 1 of the study on dentist and practice characteristics, methods and procedures used for single-unit crowns and percentage of single-unit crowns deemed acceptable, will be compared between dentists who participate in Phase I only and those who participate in Phase 2. Categorical variables will be compared using the chi-square test, and ordinal or continuous variables will be compared using the t test or Wilcoxon's rank sums test.

## 11.2 Sample Size Considerations

The primary objective (1) and (2) will be addressed using data collected from questionnaires completed by National Dental PBRN practitioners. As of June 2014, there are 2785 practitioners who reported performing nonimplant restorative procedures on the Enrollment Questionnaire. It is anticipated that approximately 1500 practitioners will complete the questionnaire. The primary measures to be calculated are percentages and confidence intervals (CIs) for prevalence of categories of response to the questionnaire items. Precision of estimation for these measures was calculated as the length of 95% CIs for a range of values of prevalence from 5% to 50%. CIs were based on the normal approximation to the binomial distribution. The maximum CI width occurs when prevalence equals 50%, with widths decreasing symmetrically on each side of this value.

Given the anticipated sample size of 1500 questionnaires, the expected total width of the 95% CI would be 5.06%, that is,  $\pm 2.53\%$ . Thus, for any value of prevalence, this sample size would provide sufficient precision to estimate the prevalence within no more than  $\pm 2.53\%$ , at the 95% confidence level. Smaller values of prevalence yield narrower expected CI widths, so that the expected CI widths for prevalence equal to 5% would be  $\pm 1.10\%$  and for prevalence equal to 10%, would be  $\pm 1.52\%$ .

The chart shows the total widths of expected 95% CIs for the proposed sample size of 1500 questionnaires, and for sample sizes of 1000, 2000, 2500 and 2785 questionnaires.

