#### 3.2 Study Outcome Measures

##### 3.2.1 *Primary Outcomes*

To estimate the percentage of single-unit crowns deemed acceptable by the practitioner at clinical try-in, the practitioner rating of crown acceptability after being returned from the laboratory for clinical try-in will be ascertained in the Stage 2 portion of the study.

A concern of this outcome measure is that it is not standardized among practitioners. Some practitioners may be very exacting, rating one crown unacceptable that would be accepted by another practitioner. However, the decision about crown acceptability is an important outcome measure for this practice-based research study, regardless of the practitioner's technical ability or clinical bias. Further, each practitioner's "clinical acceptability" level will be ascertained using a question from the questionnaire administered during Stage 1 (before the clinical component) of the study (see Section 7) as well as data from the laboratory CRF analyzing the technical aspects of the crown preparation, impression and bite registration.

To identify factors associated with practitioner acceptability of crowns, the following practice/practitioner, patient/clinical, and prosthodontics technique variables will be ascertained via a Case Report Form (CRF) administered during the crown preparation and impression appointment (during Stage 2), while the practitioner factors will be obtained from the National Dental PBRN enrollment questionnaire:

- **Practice/practitioner factors** (percentage of practice time spent doing fixed prosthodontics; whether or not the practitioner has had prosthodontic, advanced general dentistry residency, or MAGD training; years in practice; network region);
- **Patient/clinical factors** (tooth position; corono-apical position of the crown preparation margin; dentist-assessed quality of hemostasis during the crown impression; endodontic status; whether the crown has proximal contacts; type of tooth opposing the crown); crown preparation design; and

- **Prosthodontic technique factors** (impression technique; impression material; whether the person making the impression is a dentist or a dental assistant; crown preparation design; dentist-assessed quality of the opposing cast and centric jaw relation; material used for the prosthetic crown).

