The secondary objective (1) and (2) will be addressed using data collected from questionnaires completed by National Dental PBRN practitioners. As of June 2014, there are 2785 practitioners who reported performing nonimplant restorative procedures on the Enrollment Questionnaire. It is anticipated that approximately 1500 practitioners will complete the questionnaire. The primary measures to be calculated are percentages and confidence intervals (CIs) for prevalence of categories of response to the questionnaire items. Precision of estimation for these measures was calculated as the length of 95% CIs for a range of values of prevalence from 5% to 50%. CIs were based on the normal approximation to the binomial distribution. The maximum CI width occurs when prevalence equals 50%, with widths decreasing symmetrically on each side of this value.

Given the anticipated sample size of 1500 questionnaires, the expected total width of the 95% CI would be 5.06%, that is,  $\pm 2.53\%$ . Thus, for any value of prevalence, this sample size would provide sufficient precision to estimate the prevalence within no more than  $\pm 2.53\%$ , at the 95% confidence level. Smaller values of prevalence yield narrower expected CI widths, so that the expected CI widths for prevalence equal to 5% would be  $\pm 1.10\%$  and for prevalence equal to 10%, would be  $\pm 1.52\%$ .

The chart shows the total widths of expected 95% CIs for the proposed sample size of 1500 questionnaires, and for sample sizes of 1000, 2000, 2500 and 2785 questionnaires.

For the secondary objective (3) and (4), precision of estimation of the percentage of crowns rated as unacceptable by the laboratories will depend on the number of laboratories, number of crowns submitted to each laboratory, and the ICC for ratings within the same laboratory. Precision of estimation assumed 200 laboratories, each examining 20 crowns, 5% prevalence of suboptimal ratings, and ICC values of 0.0 to 0.05.

The chart presents half-widths of expected 95% CIs.

ICC	1/2 Width of 95% CI
0	0.68%
0.01	0.74%
0.02	0.79%
0.03	0.85%
0.04	0.90%
0.05	0.94%

The proposed sample size would provide estimation within  $\pm 0.68\%$  to  $\pm 0.94\%$  of a true 5% rate for this range of values of ICC.

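### Section 11.2 gives the primary percentage the precision of 1,500 Stage 1 questionnaires, although it is estimated from about 4,000 Stage 2 crowns clustered by practitioner

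*Protocol*

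**What the plan says.** Section 11.1 of the protocol states the primary objective as "Estimate the percentage of single-unit crowns deemed acceptable by the practitioner at clinical try-in, and (2) identify factors associated with crown success". It treats the first part as estimation and takes the width of the 95% confidence interval as the measure of precision.

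Section 3.2.1 fixes the data source: "the practitioner rating of crown acceptability after being returned from the laboratory for clinical try-in will be ascertained in the Stage 2 portion". The Protocol Summary and section 4 plan Stage 2 as about 200 practitioners with about 20 crowns each, 4,000 in all. Section 11.3 analyses the crown-level outcome with clustering by practitioner.

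Section 11.2 says something else: "The primary objective (1) and (2) will be addressed using data collected from questionnaires completed by National Dental PBRN practitioners". The quantities whose precision it gives are described as "The primary measures to be calculated are percentages and confidence intervals (CIs) for prevalence of categories of response to the questionnaire items". The method is simple: "CIs were based on the normal approximation to the binomial distribution". The result is "Given the anticipated sample size of 1500 questionnaires, the expected total width of the 95% CI would be 5.06" percent, that is ±2.53%, with ±1.10% at 5% prevalence and ±1.52% at 10%.

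Further on in section 11.2 the same text and figures return, introduced by "The secondary objective (1) and (2) will be addressed using data collected from questionnaires completed by National Dental PBRN practitioners".

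**The concern.** A questionnaire answered in Stage 1 cannot supply the rating of a crown that is made and tried in later, in Stage 2. The precision statement under the primary objective therefore has the wrong unit (a questionnaire, not a crown), the wrong number (1,500, not 4,000) and no allowance for clustering. All three follow from one misplaced block of text.

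Two things are at stake. Section 11.1 makes interval width the standard for the primary estimate, and the only width printed for it is not a property of the Stage 2 design. In addition, section 5.5 provides for a power (sensitivity) analysis to track whether loss to follow-up threatens the primary outcome measure. For the percentage itself the protocol gives no valid planned precision against which such a loss could be judged, because Stage 2 attrition does not change a width based on Stage 1 questionnaires.

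Clustering matters for this outcome. Section 3.2.1 itself acknowledges that practitioners differ in how strictly they judge a crown, and that is a source of within-practitioner correlation.

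**Working it through.** **Inputs, all from the protocol**

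- Questionnaires: n = 1,500 (section 11.2).
- Stage 2 crowns: 200 practitioners × 20 = 4,000 (Protocol Summary; section 4).
- Unacceptable crowns: 5% (section 11.2, power for primary objective (2)). The half-width for the percentage acceptable, 95%, is the same because p(1 − p) is symmetric.
- Variance inflation factor: VIF = 1 + (m − 1) × ICC, with ICC 0 to 0.05 (section 11.2, same place).

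**Step 1. Reproduce the printed figures.** Half-width = 1.96 × √[p(1 − p)/n], n = 1,500:

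- p = 0.50: 1.96 × √(0.25/1500) = 2.53% (total 5.06%)
- p = 0.10: 1.96 × √(0.09/1500) = 1.52%
- p = 0.05: 1.96 × √(0.0475/1500) = 1.10%

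All three match. The arithmetic is right for Stage 1 questionnaire items.

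**Step 2. The same quantity for the Stage 2 design.** Half-width = 1.96 × √[p(1 − p) × VIF/4000], VIF = 1 + 19 × ICC:

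| ICC | VIF | Effective n | Half-width, p = 0.05 | Half-width, p = 0.10 | Half-width, p = 0.50 |
|---|---|---|---|---|---|
| 0 | 1.00 | 4000 | 0.68% | 0.93% | 1.55% |
| 0.01 | 1.19 | 3361 | 0.74% | 1.01% | 1.69% |
| 0.02 | 1.38 | 2899 | 0.79% | 1.09% | 1.82% |
| 0.03 | 1.57 | 2548 | 0.85% | 1.17% | 1.94% |
| 0.04 | 1.76 | 2273 | 0.90% | 1.23% | 2.06% |
| 0.05 | 1.95 | 2051 | 0.94% | 1.30% | 2.16% |

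**Step 3. Where the two agree.** The printed widths equal the Stage 2 widths only when VIF = 4000/1500 = 2.67, so ICC = (2.67 − 1)/19 ≈ 0.088. Below that ICC the printed figures are too wide; above it they are too narrow. At 5% unacceptable, an assumed ICC of 0.10 gives ±1.15% and an assumed ICC of 0.20 gives ±1.48%. Both ICCs lie outside the protocol's range.

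**Step 4. Fewer crowns per practitioner.** The power table in section 11.2 also considers 15 crowns. With 200 × 15 = 3,000 crowns and VIF = 1 + 14 × ICC, the half-width at 5% runs from ±0.78% (ICC 0) to ±1.02% (ICC 0.05).

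**Step 5. Does another statement fill the gap?** The clustered half-width table in section 11.2 is for laboratory ratings, with the ICC within laboratory. The agreement calculation after it concerns dentist against laboratory and ignores clustering. The odds-ratio table is for primary objective (2). None gives a width for the practitioner-rated percentage.

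**The case against.** The strongest reply is that this is a duplicated paragraph with no consequence. Every figure in it reproduces. Nothing operational follows from it: section 3.2.1 places the rating in Stage 2, section 11.3 analyses crowns with practitioner clustering, and the size of 200 × 20 is supported in section 11.2 by a power calculation for primary objective (2) on clustered crowns. The laboratory table already prints 0.68% to 0.94% for 200 clusters of 20 at 5%. At 5% the misplaced ±1.10% errs on the cautious side over the protocol's whole ICC range.

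Much of this stands. The fault is a wrong data source, not a miscalculation. The odds-ratio power for primary objective (2) uses the right unit and design. The direction is conservative for ICC up to 0.05, and nothing here shows that Stage 2 is too small.

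It does not remove the point. The protocol explicitly assigns both parts of the primary objective to questionnaires, which contradicts section 3.2.1 and its own power calculation for part (2). The laboratory table coincides numerically only because the same inputs were assumed. It concerns a different rating and a different cluster, and a reader cannot be expected to transfer it. Nor is this a detail left to a statistical analysis plan: the protocol does state a precision under its primary objective, and it is that of other data.

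Section 11.1 also mentions Stage 1 information on the percentage of crowns deemed acceptable. That serves to compare dentists who take part in the first phase only with those who continue. It is not the try-in outcome.

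**Conclusion.** The point holds. Section 11.2 names the wrong data source for the primary objective, and no interval width for the primary percentage is stated anywhere in the protocol. On the protocol's own assumptions the planned half-width is ±0.68% to ±0.94%, against a printed ±1.10% at the same 5% rate and a printed maximum of ±2.53%.

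This rests on full enrolment at 200 × 20, equal cluster sizes, 5% unacceptable and an ICC of 0 to 0.05. At 15 crowns per practitioner the range is ±0.78% to ±1.02%. If the ICC exceeded about 0.088, the printed figure would overstate the precision at 200 × 20. The error is confined to the precision for part (1) and to the sentence that also sends part (2) to questionnaires.

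**What to change.** In section 11.2, delete the questionnaire paragraphs, and the sentence introducing the accompanying chart, where they stand under the primary objective. Keep them under secondary objectives (1) and (2). Put in their place, for example:

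> Primary objectives (1) and (2) use Stage 2 crowns. For (1), with 200 practitioners × 20 crowns and 5% of crowns unacceptable, the expected 95% CI half-width is 0.68% to 0.94% for an ICC within practitioner of 0 to 0.05, based on the effective sample size N/[1 + (m − 1) × ICC]. With 15 crowns per practitioner it is 0.78% to 1.02%.

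The 15-crown line is worth including because section 4 lets practitioners stop before 20 crowns and section 5.4.2 replaces no withdrawals. The power calculation for primary objective (2) can stay where it is.

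The cost is a change of protocol wording. Sample size, conduct and analysis do not change.
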